Appendix A 68GA-PSMA-11 Injection: Chemistry, Manufacturing , and Controls

STATEMENT OF COMPLIANCE

(1) The trial will be carried out in accordance with International Conference on Harmonization Good Clinical Practice (ICH GCP) and the following:

- United States (US) Code of Federal Regulations (CFR) applicable to clinical studies (45 CFR Part 46, 21 CFR Part 50, 21 CFR Part 56, 21 CFR Part 312, and/or 21 CFR Part 812)

National Institutes of Health (NIH)-funded investigators and clinical trial site staff who are responsible for the conduct, management, or oversight of NIH-funded clinical trials have completed Human Subjects Protection and ICH GCP Training.

The protocol, informed consent form(s), recruitment materials, and all participant materials will be submitted to the Institutional Review Board (IRB) for review and approval. Approval of both the protocol and the consent form must be obtained before any participant is enrolled. Any amendment to the protocol will require review and approval by the IRB before the changes are implemented to the study. In addition, all changes to the consent form will be IRB-approved; a determination will be made regarding whether a new consent needs to be obtained from participants who provided consent, using a previously approved consent form.

1 PROTOCOL SUMMARY

1.1 SYNOPSIS

Title:	Comparison of 68Ga-PSMA Positron Emission Tomography (PET)/CT to Conventional Imaging in Men with High Risk Prostate Cancer
Study Description:	This is a prospective, single-center, open-label pilot study of 68GA-PSMA-11 given at a single time prior to PET/CT imaging in men with localized high risk prostate cancer or biochemical recurrence. Eligible participants will undergo baseline assessments using conventional 99-Tc Bone Scan and CT of the Abdomen and Pelvis or multi-parametric MRI imaging of the prostate

Objectives:

Primary Objective

1. To evaluate the tissue distribution of 68GA-PSMA-11 PET/CT imaging in normal tissues and biopsy proven tumor and non-tumorous regions of the prostate, and also pelvic lymph nodes in high risk patients undergoing standard of care prostatectomy and bilateral lymph node dissection.
2. To determine the proportion of patients in which 68GA-PSMA-11 PET/CT altered the planned clinical management.

Secondary Objective:

1. To correlate the intensity of 68GA-PSMA-11 PET/CT uptake with respect to pathological findings.
2. To compare suspicious lesions visualized on 68GA-PSMA-11 PET /CT with standard of care diagnostic imaging modalities, additional biopsy results, or clinical follow-up performed at the discretion of the referring physician.

Endpoints:

Primary Endpoints:

1. Proportion of patients with cTxNoMo (clinically localized disease) found on final histological examination to have lymph node involvement as determined by 68GA-PSMA-11 PET/CT.
2. Proportion of patients in which 68GA-PSMA-11 PET/CT altered the planned clinical management.

Secondary Endpoints:

1. 68GA-PSMA-11 PET/CT intensity is variable, and we will evaluate what intensity endpoint is predictable of tissue involvement.
2. To compare and contrast findings in 68GA-PSMA-11 PET/CT with standard diagnostic modalities of bone scan, CTs and MRIs.

Study Population: Male patients, aged 21 or older, diagnosed with histopathological proven prostate adenocarcinoma, with no evidence of other malignancy, and Eastern Cooperative Oncology Group (ECOG) performance of 0-1.

Phase: Pilot, phase I/2

Description of Sites/Facilities
This is a single site trial that will be conducted at the Houston Methodist Hospital.

Enrolling Participants:

Description of Study Intervention: This is a prospective, open label, single-center, single-arm, pilot diagnostic accuracy study to evaluate the tissue distribution of 68Ga-PSMA Positron Emission Tomography (PET)/CT in 80 patients with high risk localized prostate cancer or biochemical recurrence.

Subjects will receive a single IV dose of 3-7 mCi of 68Ga-PSMA (study drug) followed by PET/CT imaging 60-90 minutes after injection. All patients will be closely monitored with vital signs (blood pressure and heart rate), before and 2 hours following radiotracer administration.

Patients will receive a phone call 2 days following PET/CT to assess for adverse events.

To minimize bias, all PET/CT images will be interpreted by a board-certified radiologist. The radiologist evaluating the images will be blinded to the final outcome, such as the histopathology of any biopsies and the outcome of subsequent imaging.

Patients with study-defined high-risk features who are eligible and scheduled for radical prostatectomy or with biochemical recurrence will undergo 68Ga-PSMA-11 PET/CT injection. The results of the 68Ga-PSMA-11 PET/CT may alter patient

management in one of several ways, including the decision to not pursue surgical extirpation (e.g. in the event of extensive distant metastasis) in favor of systemic therapy. It is also possible that the extent of surgical resection may be altered, such as non-regional pelvic or retroperitoneal lymph node dissection. The alteration in planned surgical treatment from standard of care will be recorded as a secondary-end point.

Study Duration: 18 months.
Participant Duration: 6 months.

SCHEMA

Screening
Visit 1

Total:80 patients - Obtain informed consent. Screen potential participants by inclusion and exclusion criteria; obtain history, physical exam, height/weight, ECOG, safety labs

Visit 2

Administration of study intervention.
AE assessment (Phone follow-up)

Radical Prostatectomy

Systemic Therapy to be
determined attending
physician if metastatic disease
is identified

Follow up at 2 and 6 months

Visit 3 and 4

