2.3 RISK/BENEFIT ASSESSMENT

2.3.1 KNOWN POTENTIAL RISKS

2.3.2 KNOWN POTENTIAL BENEFITS

The investigational study may determine the presence of disease outside of the prostate that is resectable at the time of the surgery and that may improve long term outcomes.

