8.8 Prostatectomy

Subjects will undergo standard of care surgery as deemed appropriate by the patient's attending urologist.

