8.9 Surgical Pathology

Following radical prostatectomy and/or pelvic lymph node dissection, surgical specimens will be brought on ice to the Department of Surgical Pathology for tissue processing. Prostatectomy and lymph node specimens will be processed by the Department of Pathology in the standard fashion with hematoxylin and eosin (H&E) staining for grading and staging. Additionally, immunohistochemistry will be performed to confirm, at a microscopic level, that radiolabeled 68Ga-PSMA-11 co-localizes with tumor foci seen on H&E sections. Tumor foci identified on H&E sections will serve as the gold standard for imaging comparison.

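### The PET result may extend the node dissection, and primary endpoint 1 sets no common node region, so histology may be more extensive in operated PET-positive men; read as a sensitivity, the endpoint can be inflated.

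*Combined protocol and SAP*

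**What the plan says.** The synopsis (1.1, Description of Study Intervention) gives two ways in which the PET result may change surgery. It may lead to "the decision to not pursue surgical extirpation (e.g. in the event of extensive distant metastasis) in favor of systemic therapy". Alternatively, "It is also possible that the extent of surgical resection may be altered, such as non-regional pelvic or retroperitoneal lymph node dissection". Section 2.3.2 presents the second route as the potential benefit: the study "may determine the presence of disease outside of the prostate that is resectable at the time of the surgery".

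Primary endpoint 1 (1.1 and section 3) is: "Proportion of patients with cTxNoMo (clinically localized disease) found on final histological examination to have lymph node involvement as determined by 68GA-PSMA-11 PET/CT". It does not say which nodes count. The matching objective is narrower. It concerns pelvic nodes in "patients undergoing standard of care prostatectomy and bilateral lymph node dissection".

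No section standardises the dissection. Section 8.8 says "Subjects will undergo standard of care surgery as deemed appropriate" and leaves that judgement to the attending urologist. No template, minimum node count or blinding of the surgeon to PET is stated. Section 8.9 begins "Following radical prostatectomy and/or pelvic lymph node dissection", so a node dissection is not assured for every man; section 9.1 also uses and/or. The blinding in sections 4.1 and 6.3 covers only the PET reader, and only as to outcome. Section 9.3 plans descriptive statistics, with no rule for unequal dissection.

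**The concern.** In a diagnostic accuracy study the reference standard should not depend on the index test. Here it can. Where PET shows uptake outside the usual field, the surgeon may remove nodes there and pathology will examine them. Comparable disease in a PET-negative man stays in place, and he is counted as node-negative. Among operated men, missed disease is then more likely to be found if PET was positive, so false negatives are under-counted relative to true positives.

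Endpoint 1 is exposed because its wording admits any node, although objective 1 concerns pelvic nodes at standard dissection. The study describes itself as a diagnostic accuracy pilot whose results will support later studies (4.1, 4.2). A sensitivity raised partly by the surgery would be carried into them.

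**Working it through.** The plan has no figure to reproduce: section 9.1 says the sample size was not statistically determined, and no node prevalence, PET sensitivity or extension rate is given. Every rate below is an assumption.

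**Inputs.** s = true per-patient sensitivity of PET, 60%. d0 = chance that a standard dissection finds existing nodal disease, 50%, 65% or 80%. d1 = the same for a PET-extended dissection, 95%. e = share of node-positive PET-positive men who are extended. q = share of those men whose surgery is cancelled, taken as zero at first.

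**Step 1: apparent sensitivity.** Average capture in PET-positive men is c = (1 − e)·d0 + e·d1. In PET-negative men it is d0. Apparent sensitivity = s·c / [s·c + (1 − s)·d0].

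Example with e = 25%, d0 = 80%: c = 0.75 × 0.80 + 0.25 × 0.95 = 0.8375, and 0.60 × 0.8375 / (0.60 × 0.8375 + 0.40 × 0.80) = 0.5025 / 0.8225 = 61.1%.

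| Share extended (e) | d0 = 80% | d0 = 65% | d0 = 50% | Inflation over 60% |
|---|---|---|---|---|
| 0% | 60.0% | 60.0% | 60.0% | 0 |
| 10% | 60.4% | 61.1% | 62.0% | 0.4-2 points |
| 25% | 61.1% | 62.6% | 64.8% | 1-5 points |
| 100% | 64.0% | 68.7% | 74.0% | 4-14 points |

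With all extended, true sensitivities of 50% and 70% give 54.3-65.5% and 73.5-81.6%.

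**Step 2: other readings of endpoint 1.** Let π be the true node prevalence, and assume histology gives no false positives.

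- Joint PET-positive/histology-positive yield is π·s·c, which cannot exceed the true π·s because c is at most 1. With π = 30%, s = 60%, d0 = 70%, it rises from 12.6% (none extended) to 17.1% (all extended); the truth is 18%. With π = 20%, s = 40%, d0 = 85%, it rises from 6.8% to 7.6%; the truth is 8%.
- Observed positive predictive value is the true value times c, so it too moves towards the truth from below.
- The overall histological node-positive rate is π·[s·c + (1 − s)·d0]. In the first case it rises from 21.0% to 25.5%, against a true 30%.

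Only the sensitivity reading is inflated above the truth.

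**Step 3: cancelled surgery.** If cancelled men have no nodal histology and drop out, c is replaced by (1 − q)·c. The extension effect is fully offset when (1 − q)·c = d0, that is q = 1 − d0/c.

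- All extended: q = 1 − 0.80/0.95 = 16% at d0 = 80%, and 1 − 0.50/0.95 = 47% at d0 = 50%.
- 25% extended: q = 1 − 0.80/0.8375 = 4%, and 1 − 0.50/0.6125 = 18%.

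The documents give neither e nor q, so the net sign over all enrolled men cannot be determined.

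**Step 4: scale.** The 80 men include biochemical recurrence, so 80 is an upper bound for the operated group. At 20-30% prevalence there would be at most 16-24 node-positive men, and one man is worth about 4-6 points of sensitivity (1/24 to 1/16). As a proportion of all men, 16/80 = 20% has a 95% Clopper-Pearson interval of 11.9-30.4%.

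**The case against.** The strongest reply is that the effect is small and may not occur. The synopsis says only that the extent may be altered, and its examples suggest uptake outside the usual field. Nothing says that a man whose PET is positive inside the standard field has a wider operation. At 10-25% extended, the inflation is about the weight of one man or less, in a descriptive pilot with no hypothesis test. All of this stands, and it limits the size of the point. It does not supply the missing rule.

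A reader might infer that PET-positive men as a group will have more nodes examined, or that yield, sensitivity and predictive value all move in PET's favour. The documents do not support either. The first turns a possibility into a fact and overlooks the preceding sentence of the synopsis, under which some PET-positive men have no nodal histology at all. The second fails in step 2, where yield and predictive value only approach the truth. Nor is pathology itself more thorough after a positive PET: section 8.9 processes all specimens in the same way, and only the amount of tissue can differ.

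It can also be said that the plan already covers part of this. Altered surgical plans are to be recorded (1.1), altered management is primary endpoint 2, PET node locations are recorded in seven sub-categories (4.1, 8.7.1), and retroperitoneal nodes arguably fall outside objective 1. That makes the fix cheaper. However, endpoint 1 does not use any of these records, and non-regional pelvic nodes remain open.

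**Conclusion.** The point holds in a limited form. The index test can decide how much nodal tissue reaches the reference standard, and neither the endpoint definition nor the analysis guards against it. The harm is confined to operated men and to the reading of endpoint 1 as the share of histologically node-positive men whom PET identified. Under the assumed rates (true sensitivity 60%, standard capture 50-80%, extended capture 95%) the inflation is about 0.4-2 points with 10% of node-positive PET-positive men extended and 1-5 points with 25%. The 4-14 point range needs every such man to be extended, and its upper end also needs a standard dissection to miss half of node-positive men; no figure in the documents supports either. Over all enrolled men the direction is open, because cancelled surgery works the other way. Two unmeasured effects in opposite directions are not a safeguard, so a scoring rule is worth adding.

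**What to change.** - Score endpoint 1 within one pre-specified pelvic node region, for example the six named node sub-categories in sections 4.1 and 8.7.1 (leaving out Other), in men who had nodes from that region removed. Name the region explicitly, because objective 1 defines no template and sections 8.9 and 9.1 do not assure a dissection for every man.
- Apply the same region to the PET read and to the histology. If only the histology were restricted, a man with a confirmed node outside the region could be scored as a PET false positive.
- Report nodes removed only because of PET in a separate line (number sampled, number positive), with an all-nodes version of the endpoint beside it.
- Record on the CRF which packets were added because of PET. This would also show any PET-driven difference inside the region, which the region rule alone does not remove.
- State how many men had no nodes from the region examined, by PET result, so that the effect of cancelled surgery is visible.

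The cost is a short endpoint definition, the choice of region and one CRF item. Surgical decisions are unchanged. The small downside is that the primary proportion may be slightly lower and leaves out spread beyond the region, which section 3 wants captured; the separate line and the all-nodes version report it.

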1.2 SCHEDULE OF ACTIVITIES (SOA)

The schedule below is provided as an example and should be modified as appropriate.

	Screening	Enrollment	Post Dose		Surgery/Pre-surgery Follow up/Early Termination	Follow up	Follow up
	Day -28 to 0	Day 0	Day 0: Hour 1-2	Day 2	Day 10 +/- 7	Month 2 +/- 7	Month 6 +/- 7
	Visit 1	Visit 2		Phone call		Visit 3	Visit 4
Informed Consent	R						
Demographics	R						
Inclusion/Exclusion Criteria	R						
Medical History ¹	R						
Performance Status	R						
Vital Signs ²	R		R ³				
Administer Study Intervention 68Ga PSMA 11		R					
Whole body PET/CT		R					
PSA	R					SOC	SOC
Bone Scan ⁴	SOC						
CT abdomen/pelvis ⁴	SOC						
MRI of prostate	SOC						
Adverse event evaluation			R	R	R		
Prostate Biopsy	SOC						
Telephone call				R			
Prostatectomy					SOC		

Pathology processing					SOC	
----------------------	--	--	--	--	-----	--

¹ *Medical history includes review of prostate cancer treatment and prior radiographic exams.*

² *Vital Signs Assessment includes measurement of blood pressure and heart rate.*

³ *On days of dosing, vital signs will be collected pre-dose and post-dose.*

⁴ *If not performed within 6 months of Screening, diagnostic CT or MR scans and or Bone scan are to be obtained prior to surgery, only if clinically indicated*

2 INTRODUCTION

2.1 STUDY RATIONALE

Prostate cancer (PCa) remains the most common non-cutaneous cancer diagnosis in males, with an estimated 174,650 new cases in 2019[2]. After lung cancer, PCa accounts for the second highest mortality in men. Localized PCa, often screen-detected using prostate specific antigen (PSA) based blood tests, is highly variable in clinical course and risk of progression. Treatment is therefore matched on this basis, and includes Active Surveillance for Low-Risk PCa, whereas Intermediate- and High-Risk PCa are treated by radiation therapy (external beam or brachytherapy) or surgery (radical prostatectomy). While durable cure can be achieved by these modalities, biochemical relapse occurs in approximately 35% of who have undergone treatment for localized disease[3].

There is significant interest in identifying individuals at highest risk of biochemical relapse, using a variety of approaches, including genomic-based biomarkers. Identification of metastatic disease beyond of the prostate is critical, not only for potentially targeted local-therapy (e.g. surgical resection of recurrence or targeted radiation therapy) but earlier use of aggressive adjuvant radiation or systemic therapies. Imaging based identification of low volume disease outside of

the prostate has been limited by the sensitivity of cross-sectional tomography (CT), which relies on nodal morphology (size). The sensitivity of CT or MRI based imaging for the detection lymph node metastasis is in the range of 30-80%[4]. Detection of bone metastasis once present as osteoblastic lesions can be identified by bone-scintigraphy, again with limited sensitivity, especially in asymptomatic patients with PSA levels below 20[5]. In spite of these limitations, CT and whole body bone scans are widely accepted as the primary imaging modality for staging patients, particularly with localized PCa.

2.2 BACKGROUND

Molecular imaging using various targets and positron emission tomography (PET) tracers have been used to improve detection of recurrent prostate cancer. ¹⁸F- or ¹¹C labeled choline as well as ¹¹C-acetate have been previously investigated[6,7]. Their clinical utility has been limited by non-specific uptake in benign tissue, including benign prostatic hypertrophy[8]. ¹⁸F-Fluciclovine has recently been approved owing to its improvement over ¹¹C[9]. Targeting of prostate-specific membrane antigen (PSMA) by radiotracer has gained the most contemporary clinical interest. PSMA (glutamate carboxypeptidase II, N-acetyl- α -linked acidic dipeptidase I, or folate hydrolase) is a type II transmembrane glycoprotein belonging to the M28 peptidase family is preferentially overexpressed in prostate cancer cells relative to other cells. Other tissues may also express PSMA, including kidney, small intestine or salivary glands. Importantly, PSMA expression is maintained and may increase through the full spectrum of prostate cancer, including advanced disease[10].

Methods have focused on labeling ligands (Glu-NH-CO-NH-Lys-(Ahx)-[⁶⁸Ga(HBED-CC)] also known as ⁶⁸-PSMA-11) to PSMA with ⁶⁸-Ga, allowing internalization and significant differential contrast between normal and cancerous tissues which aids in optimal imaging characteristics[11,12]. Initial studies showed that labeling of PSMA-ligand with ⁶⁸-Ga allowed improved identification of PCa recurrence and metastasis [13].

Early data has demonstrated the utility of ⁶⁸Ga-PSMA with respect to improved accuracy of detection and in turn significant impact on treatment decisions[14]. A recent meta-analysis of ⁶⁸Ga-PSMA PET studies showed promising detection of metastasis following biochemical recurrence, even at low PSA levels [PSA >0.2

ng/ml (33% detection rate) and PSA 0.2–0.5 ng/ ml (45% detection rate)][15]. Importantly, the vast majority of these studies have been reported from retrospective data.

In our study we plan to prospectively study the accuracy and utility of 68Ga-PSMA 11 and its impact of the treatment related decisions.

2.3 RISK/BENEFIT ASSESSMENT

2.3.1 KNOWN POTENTIAL RISKS

2.3.2 KNOWN POTENTIAL BENEFITS

The investigational study may determine the presence of disease outside of the prostate that is resectable at the time of the surgery and that may improve long term outcomes.

2.3.3 ASSESSMENT OF POTENTIAL RISKS AND BENEFITS

- **Study Imaging Drug Risk:** Possible side effects such as rash, nausea, headache or fatigue. In clinical studies that used 68Ga-PSMA-11 in the same amount being used in this study, no serious adverse events were reported.
- **PET/CT scan radiation risk:** the maximum amount of radiation from this study is equivalent to 2.43 mSv and less than 1 mSv for non-diagnostic CT scan performed to process the PET data. The total radiation dose from the study procedure is less than 1/10th the annual exposure allowed for occupational workers. Although there are no proven harmful effects from this amount of radiation, long-term effects, such as cancer, cannot be ruled out with certainty. This dose estimate takes into account only the exposure to research procedures in this study.
- **Other risk:** pain and infection at the site of the needle stick for the study drug injection or for blood drawn for the blood tests.

3 OBJECTIVES AND ENDPOINTS

OBJECTIVES	ENDPOINTS	JUSTIFICATION FOR ENDPOINTS
Primary		

 1. To evaluate the tissue distribution of 68GA-PSMA-11 PET/CT imaging in normal tissues and biopsy proven tumor and non-tumorous regions of the prostate, and also pelvis lymph nodes in patients undergoing standard of care prostatectomy and bilateral lymph node dissection in high risk patients 2. To determine the proportion of patients in which 68GA-PSMA-11 PET/CT altered the planned clinical management 	
 1. Proportion of patients with cTxNoMo (clinically localized disease) found on final histological examination to have lymph node involvement as determined by 68GA-PSMA-11 PET. 2. Proportion of patients in which 68GA-PSMA-11 PET/CT altered the planned clinical management. 	
 1. Determining the usefulness of PSMA PET/CT requires defining its' ability to identify lymphatic or metastatic spread that heretofore has not been detectable by standard radiographic means. 2. Understanding whether and why 68GA-PSMA-11 PET/CT findings alter treatment plans is critical in defining its role in the diagnostic tools urologists use to manage their patients with prostate cancer.
Secondary		

 1. To correlate the intensity of 68Ga-PSMA-11 uptake 	
 1. 68Ga-PSMA-11 PET/CT intensity is variable, and we will evaluate 	
 1. To identify those patients in whom more localized or extended therapy might be indicated, it is important

OBJECTIVES	ENDPOINTS	JUSTIFICATION FOR ENDPOINTS

with respect to pathological findings.
 
2. To Compare suspicious lesions visualized on 68Ga-PSMA-11 PET/CT with standard of care diagnostic imaging modalities, additional biopsy results, or clinical follow-up performed at the discretion of the referring physician
	
what intensity endpoint is predictable of tissue involvement.
 
2. To compare and contrast findings in 68Ga-PSMA-11 PET/CT with standard diagnostic modalities of bone scans, CTs and MRIs
	
to know in equivocal 68Ga-PSMA PET/CT readings what the true positive results histopathologically are in order to avoid possible over / under treatment.
 
2. Based on histologic results comparing standard radiographic modalities to 68Ga PSMA 11 PET/CT findings will add value as to whether they are complimentary or one or more might be deleted in the workup of these men.

